## 1. History of preparation and revision

Version number	Date of preparation/revision	Prepared/Revised by	Reasons
1.0	2/8/2017	[REDACTED]	The first version
1.1	4/6/2017	[REDACTED]	
 
■ 2.Definition of terms and abbreviation 
 
● Patients who were followed up for 52 weeks (patients collected for the first volume), Patients who were followed up for 104 weeks (patients collected for the first/second volume), patients who were followed up for 156 weeks (patients collected for the first/second/third volume)
 
 
 
■ 8.Definition of population used for analysis 
 
● Definition of registered patients to delete the definition of registered eligible patients and registered not eligible patients
 
● Definition of patients for whom data of the survey sheet was not fixed was changed
 
 
 
■ 10.1 Overall 
 
● Added a description,“ The test is deemed to have been performed if a box is not checked but laboratory test results are described” to a definition of implementation of “Test for tuberculin reaction or IGRA”
 
● Added definitions of “Patients excluded from separate volume”, “Chest X-ray or CT scanning”, “Test for tuberculosis”, “Test for Hepatitis B”, and “Responding patients”
 
 
 
■ 12.2 Time of evaluation of occurrence
 

Version number	Date of preparation/revision	Prepared/Revised by	Reasons
			
status of adverse reaction
 
 
● Deleted evaluation time 2 and 3 to change items for time of evaluation
 
 
■ 13.1 Overall
 
 
● Changed purpose of analysis and analysis items of 1.1.1, 1.6, 1.7.1, and 1.12.1
 
● Added a description of 1.4.3
 
 
Deleted 1.5 and 1.6.1
 
 
● Changed items subject to analysis for 1.13
 
 
■ 13.2 Safety
 
 
● Changed analysis items of 2.4.1, 2.4.2, 2.4.3, and 2.9
 
● Added descriptions of 2.7, 2.19.1, and 2.19.2
 
● Deleted 2.7(1), 2.7(2), 2.7(3), 2.8(1), 2.8(2), 2.8(3), and 2.19
 
● Added a description of 2.9.xx
 
 
■ 13.3 Efficacy
 
 
● Changed analysis item of 3.4
 
● Changed a method of description to that by which the contents of 3.5 are divided into 3.5.1 and 3.5.2.
 

1.2	11/1/2017	[REDACTED]	
■ 10.1 Overall
 
Changed the method of description so that condition drawing for “presence or absence of previously used drug (aminosalicylic acid preparation)”, “presence or absence of previously used drug (steroid)”, “presence or absence of previously used drug (immunomodulative drug)”, “presence or absence of previously used drug (antibiotics)”, and “presence or absence of previously used drug (others)” can include information in the check box in survey sheet.

## 2. ■ 2. Definition of terms and abbreviations

Terms and abbreviations used in this analysis plan are defined as follows:

Terms and abbreviations	Definition
Patients who were followed up for 52 weeks (patients collected for the first volume)	Patients who started to receive this drug between August 16, 2014 and August 15, 2015.
Patients included at the 104th week of follow-up (patients collected for the first and second volume)	Patients who started to receive this drug between August 16, 2013 and August 15, 2014.
Patients included at the 156th week of follow-up (patients collected for the first, second, and third volume)	Patients who started to receive this drug by August 15, 2013.
Adverse events	Any unfavorable and unintended sign (including an abnormal laboratory finding), symptom, or disease, regardless of whether they are related to this drug or not
Adverse events that occurred during the period subject to safety analysis	
Adverse events that occurred from the start date of administration until the time as follows should be included.
 
 
Patients included at the 52th week of follow-up: The start date of administration of this drug + 392 days (56 weeks)
 
Patients included at the 104th week of follow-up: The start date of administration of this drug + 756 days (108 weeks)
 
Patients included at the 156th week of follow-up: The start date of administration of this drug + 1120 days (160 weeks)
 
Patients who discontinued to receive this drug: The last date of administration of this drug + 28 days
 

Adverse events that occurred in a period except for the period subject to safety analysis	
Adverse events that occurred before the start date of administration or after the following timing should be included
 
 
Patients included at the 52th week of follow-up: The start date of administration of this drug + 392 days (56 weeks)
 
Patients included at the 104th week of follow-up: The start date of administration of this drug + 756 days (108 weeks)
 
Patients included at the 156th week of follow-up: The start date of administration of this drug + 1120 days (160 weeks)
 
Patients who discontinued to receive this drug: The last date of administration of this drug + 28 days
 

Adverse reaction	Among adverse events, those for which causal relationship with this drug cannot be ruled out should be included
Adverse reactions that occurred during the period subject to safety analysis	Among adverse events that occurred during the period subject to safety analysis, those for which causal relationship with this drug cannot be ruled out should be included
Adverse reactions that occurred outside the	Among adverse events that occurred outside the specified safety analysis period, those for which causal relationship with this drug

Terms and abbreviations	Definition
specified safety analysis period	cannot be ruled out should be included
Summary statistics	The number of patients, mean value, standard deviation, the minimum value, the first quartile point, median value, the third quartile point, and the maximum value should be applicable
MedDRA/J	Medical Dictionary for Regulatory Activities / Japanese edition(ICH MedDRA/J)
SOC	System Organ class in MedDRA/J
PT	Preferred Term in MedDRA/J
LLT	lower Level Term in MedDRA/J
IGRA test	Interferon $\gamma$ free release test
GB	Green Book Guidance for application for reassessment

### 3. Purpose of this statistical plan

#### 3.1. Purpose of preparation of this statistical plan

Main purpose of this statistics plan is to define items used for operations of statistical analysis conducted according to implementation plan of “Special use result survey of HUMIRA® subcutaneous injection (all case survey concerning gastro-intestinal Behcet disease)” (hereinafter referred to as “this survey”). This survey is one of surveillance conducted according to GPSP ordinance, and a part or all of the analysis results serves as material for reporting of special use result survey of this drug to regulatory authority and for preparation of application for reassessment.

### 4. Outline of survey

#### 4.1. Objective of survey

Objective of this survey is to understand following matters when HUMIRA® subcutaneous injection (hereinafter referred to as “this drug”) is used in patients with gastro-intestinal Behcet disease.

- 1) Unknown adverse reactions (especially important adverse reactions)
- 2) Occurrence status of adverse reactions under actual use conditions
- 3) Factors that may contribute to safety and efficacy

<<Primary survey items>>

Infection, tuberculosis, interstitial pneumonia, malignant tumour, cardiac failure congestive, pancytopenia, autoimmune disease, demyelinating disorder, and administration site reaction

#### 4.2. Planning of survey

Any patients with gastro-intestinal Behcet disease (only those who did not respond to existing treatment) who receive this drug for defined indication for use and dosage and administration are included.

#### 4.3. Scheduled number of patients included in this survey

Not decided

All patients with gastro-intestinal Behcet disease are registered after the approval of this drug for use in patients with gastro-intestinal Behcet disease.

All case survey is decided to be conducted because approval of this drug for treatment of gastro-intestinal Behcet disease in Japan is the first in the world and the clinical trial was open-label trial including only 20 patients. In order to make reporting after reassessment period, follow-up period requires at least 52 weeks per patient, and therefore, we set the registration period as 2 years and 6 months after the date of approval for additional indication for use. Registration after 2 years and 6 months had passed should be continued for only patients who use this drug.

### 5. Items subject to analysis and the method

#### 5.1. Analysis items

##### 1) Items related to patient distribution

- [1] The number of registered patients
- [2] The number of patients for whom a survey sheet data was fixed
- [3] The number of patients included in safety evaluation
- [4] The number of patients included in efficacy evaluation

##### 2) Items related to safety

- [1] List of occurrence status of adverse reactions and infections
- [2] Factors that may contribute to safety
  - Incidence of adverse reactions by patient characteristics (sex, disease duration, smoking habit, presence or absence of complications, presence or absence of medical history, presence or absence of allergy, presence or absence of previous treatment, and presence or absence of concomitant drugs)
  - According to symptoms of Behcet disease other than gastrointestinal tract symptoms
  - According to changes in steroid dose in patients who receive steroid
- [3] Adverse events that occurred during or after administration of this drug

- List of occurrence status of serious adverse events

[4] Occurrence status of Self-administration error

[5] Contribution to safety when anti-adalimumab antibody is detected

3) Items related to efficacy

[1] Comprehensive evaluation of gastrointestinal symptoms, evaluation of gastrointestinal symptoms Behcet disease, evaluation of main symptoms of Behcet disease, evaluation of accessory symptoms, level of improvement in endoscopy findings, and CRP

[2] Factors considered to contribute to efficacy

- Efficacy by patient characteristics (sex, disease duration, smoking habit, presence or absence of complications, presence or absence of medical history, presence or absence of allergy, presence or absence of previous treatment, and presence or absence of concomitant drugs)
- According to symptoms of gastro-intestinal Behcet disease
- According to changes in steroid dose in patients who receive steroid
- Contribution to efficacy when anti-adalimumab antibody is detected

4) Items concerning patients with specific characteristics

List of occurrence status of adverse reactions/infections in patients with specific characteristics including children, the elderly, expectant and nursing mothers, patients with renal impairment, or patients with hepatic function disorder

## 5.2. Method of analysis

Appropriate method including chi-square test should be used according to scale and property of analysis

## 6. Implementation status of analysis and the schedule

Objective of analysis	Survey period and deadline for reassessment
The 6th safety periodic report	Between January 1, 2016 and December 31, 2016
Reassessment	Between May 16, 2013 and May 15, 2017

## 7. Software and dictionary used for analysis

### 7.1. Software for statistical tabulation and analysis

Information about software and its version used for analysis is described as

follows:

	Software and its version
OS	Microsoft Windows 7 or newer version should be used
Software for statistical analysis	SAS Ver. 9.2 or newer version should be used
Software for statistical tabulation	Microsoft Excel 2010 or newer version should be used

## 7.2. Dictionary used for analysis

Dictionary used to express term of adverse events, complications, and name of drugs is described as follows:

Items	Name of dictionary and its version	Remarks
Types of adverse events and adverse reactions/infections	ICH Medical Dictionary for Regulatory Activities (MedDRA/J version 19.1)	
 
After the events are classified into system organ class (SOC), appropriate terms should be chosen and written among preferred term (PT).
 
When term of the events are displayed as SOC, order according to international consensus should be followed.
 
Version of MedDRA/J used should be described in the blank space
 

Name of drug (concomitant drug)	Pharmaceutical product name data file *Appropriate version should be used for data aggregation according to the timing of analysis	
 
Seven digit code should be used for aggregation of concomitant drugs by drug in principle
 
The lowest level code should be used as priority for a list of concomitant drugs
 

## 8. Definition of population used for analysis

Name of population	Definition
Patients who were transferred to another institutions	Patients registered at different institutions in duplicate are applicable.
Registered patients	Patients who are eligible for registration based on registration assessment are applicable.
Not registered patients	Patients not registered for whom survey sheet data was collected are applicable.
Patients for whom a survey sheet data was fixed	Patients for whom a survey sheet data was fixed are applicable.
Patients for whom a survey sheet data was not fixed	Patients for whom a survey sheet data was not fixed are applicable. As a reason for unfixed survey sheet, “patients for which survey sheet cannot be collected” should be chosen for applicable patients extracted from “[HUMIRA BD] Patients whose survey

Name of population	Definition
	sheet cannot be collected.xls”
Patients excluded from safety analysis	
Patients corresponding to exclusion conditions for safety analysis are applicable. For exclusion conditions for safety analysis, standard data “Adoption or not adoption of patients” should be referred to.
 
Items of exclusion are as follows:
 
 
• Violation of contract: Institutions/departments with which contract is not concluded
 
• Physicians outside the contract
 
• Period excluded from survey period
 
• Patients who have not received this drug
 
• Patients without physician’s evaluation
 
• Duplicated patients
 
• Patients who were transferred to another institutions
 
• Patients in whom safety cannot be assessed
 
• Patients who received this drug before the contract
 

Patients included in safety analysis	Patients included in those for whom survey sheet was fixed after excluding those excluded from safety analysis
Patients excluded from efficacy analysis	
Patients corresponding to exclusion conditions for efficacy analysis are applicable. For exclusion conditions for efficacy analysis, standard data “Adoption or not adoption of patients” should be referred to.
 
Items of exclusion are as follows:
 
 
• Patients with diseases which is not subject to the survey
 
• Patients in whom efficacy cannot be assessed
 

Patients included in efficacy analysis	Patients included in those for whom survey sheet was fixed after excluding those excluded from efficacy analysis

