(21) Outcome

Outcome with the first priority among “Outcome” according to definition of “10.2 safety analysis” for PT code output as adverse reaction should be applied. This item should be left as blank if “absent” is chosen as description for presence or absence.

(22) Survey sheet number

Patient number described in this survey sheet should be applied.

(23) Withdrawn

Patients who were excluded from safety analysis and those excluded from efficacy analysis are defined as “patients withdrawn from both analysis”.

Patients excluded from safety analysis except for patients defined as above are defined as “patients withdrawn from safety analysis”.

Patients excluded from efficacy analysis except for patients defined as above

are defined as “patients withdrawn from efficacy analysis”.

Notes: For items subject to aggregation, if the number of relevant data is 0, “0” should be output without leaving it as blank.

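### Section 8 removes duplicated, transferred and out-of-contract records from the safety set but, as written, not from the efficacy set

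*SAP*

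**What the plan says.** SAP Section 8 builds two analysis sets in parallel from the same base, patients with a fixed survey sheet.

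- Safety set: "Patients included in those for whom survey sheet was fixed after excluding those excluded from safety analysis". Nine exclusion items follow, among them "Duplicated patients", patients transferred to another institution, "Patients who have not received this drug", and several contract and survey-period violations. The first row of the same table defines transferred patients as double registrations: "Patients registered at different institutions in duplicate are applicable".
- Efficacy set: "Patients included in those for whom survey sheet was fixed after excluding those excluded from efficacy analysis". Two exclusion items are listed: "Patients with diseases which is not subject to the survey" and "Patients in whom efficacy cannot be assessed".

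Both rows also point to a standard data file, *Adoption or not adoption of patients*, for the exclusion conditions. That file is not part of the SAP. Table 2.3 item (23) codes withdrawn patients in three groups: withdrawn from both analyses, from safety only, and from efficacy only.

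**The concern.** Most of the nine safety items are not about safety. A duplicate is a duplicate for any endpoint, and a record from a site without a contract is no more admissible for efficacy than for safety. If the efficacy set omits these exclusions, three things follow.

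- A person with two rated records is counted twice in numerators and denominators. For a transferred patient there may also be two last follow-up ratings, although Section 12.3 assumes one per patient.
- Fisher's exact test and the Mann-Whitney test in Table 3.4 assume independent patients. That table serves a stated survey objective, to find factors that may contribute to efficacy.
- Safety and efficacy results in the same report would describe different patients for reasons unrelated to either outcome.

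**Working it through.** **Step 1. Set the two lists side by side (Section 8).**

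| Reason | In safety list | In efficacy list | Can count a person twice |
|---|---|---|---|
| Duplicated | yes | no | yes |
| Transferred (registered at two institutions) | yes | no | yes |
| No contract, physician outside contract, treated before contract | yes | no | no |
| Outside the survey period | yes | no | no |
| Never treated | yes | no | no |
| No physician's evaluation | yes | no | no |
| Safety not assessable | yes | no | no |
| Disease outside the survey | no | yes | no |
| Efficacy not assessable | no | yes | no |

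The third line covers three items, so the safety list has nine and the efficacy list two. They share none. No sentence in Section 8 or Section 13.3 says that the efficacy set is drawn from the safety set.

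**Step 2. Which tables can be affected?**

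- *Duplicated or transferred, with two fixed and rated sheets.* Neither efficacy exclusion catches them. They enter Tables 3.1 and 3.4, and Tables 3.1.1 to 3.6 wherever an evaluation falls in the window.
- *Out of contract or out of period, with a rating.* They stay in the same tables, each counted once.
- *Untreated.* The windows in Section 12 count from the first dose, and Tables 3.1.1 to 3.6 admit only patients with the required in-window evaluation. Without a dose date there is no day 1, so these patients cannot enter. Tables 3.1 and 3.4 state no such filter, and Section 9.2 keeps unknown values in rate denominators. An untreated patient could therefore remain in those two denominators and in the efficacy-set columns of Tables 1.6 and 1.12.1, unless removed as not assessable for efficacy, a term the SAP does not define.

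**Step 3. Size.** The SAP gives no counts, and Section 4.3 sets no planned number, so there is no figure to reproduce. Let f be the share of the efficacy set that should have been removed, p the response rate in the rest, and q the rate in the retained records:

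observed rate = (1 − f)p + fq, so shift = f(q − p).

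With q anywhere from 0 to 1, the shift lies between −fp and +f(1 − p). Taking p = 60% or 80% as assumptions, each percentage point of f moves the rate by:

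- p = 60%: −0.6 to +0.4 points
- p = 80%: −0.8 to +0.2 points

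Purely as an illustration, f = 5% turns 60% into 57.0% to 62.0%, and 80% into 76.0% to 81.0%. If q = p the shift is zero.

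For a single duplicate added to N persons with R responders, the shift is (R + x)/(N + 1) − R/N = (x − R/N)/(N + 1), where x is 1 if the duplicate is rated a responder and 0 otherwise. The bias in a rate is small. The tests still treat two records of one person as two independent patients, whatever the shift.

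**The case against.** The strongest counter-argument is the unseen file. Section 8 sends the reader to it for the exclusion conditions of both sets, and it may flag duplicates and contract cases as not adopted for efficacy too. This stands as a limit: the text shows what the stated rule does, not what the programming did. It does not clear the text, because Section 8 goes on to list the exclusion items and gives two for efficacy. If the file applies more, the list is wrong.

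Separate safety and efficacy populations are also a legitimate choice. A patient whose safety cannot be assessed may still have a valid efficacy rating. That stands too, and it argues against defining the efficacy set as a subset of the safety set.

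Four stronger readings are tempting but not supported.

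- A reader might infer that untreated patients sit in every efficacy rate. The dose-based windows rule this out for Tables 3.1.1 to 3.6.
- A reader might take item (23) of Table 2.3 as proof of retention. Its safety-only category is consistent with retention, but a three-way code list can have an empty category.
- A reader might say that contract violations break independence. They may be distinct, treated patients; the issue there is eligibility, not double counting.
- A reader might attach a percentage to the contamination. The SAP gives no basis for one.

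Finally, the named primary survey items in Section 4.1 are all safety events, and the Table 3.4 tests are unadjusted factor screening. This lowers the stakes but does not remove the error.

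**Conclusion.** The point holds as a wrongly stated rule. Read literally, Section 8 leaves duplicated and transferred records, and rated out-of-contract or out-of-period patients, in the efficacy set. Only the first two can double-count a person and disturb the Table 3.4 tests, and only where both records have fixed and rated sheets. Untreated patients matter at most for the denominators of Tables 3.1 and 3.4 and the efficacy columns of Tables 1.6 and 1.12.1.

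The size is unknown. It depends on the number of such records, which the SAP does not report, and on how they were rated. The conclusion also assumes that the referenced file adds nothing to the printed list; if it does, the fault is a misdescribed population instead. It should be fixed, but it does not by itself invalidate the efficacy results.

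**What to change.** In the efficacy row of Section 8, state that the record-validity exclusions also apply to efficacy: duplicated patients, transferred patients, untreated patients, and contract and survey-period violations. Add a rule for keeping one record per person where appropriate. Keep inability to assess safety as a safety-only reason, and say explicitly whether patients without a physician's evaluation are excluded from efficacy. Check the printed list against the *Adoption or not adoption of patients* file and bring the two into agreement.

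Then align Table 2.3 item (23), so that a patient with one of these reasons is coded as withdrawn from both analyses, and show the same reasons in the efficacy branch of Figure 1.1.

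The cost is one added statement in Section 8, a minor programming change, and a slightly smaller efficacy denominator if any such records exist.

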## 9. General arrangements for analysis

### 9.1. Handling of missing data

When analysis is conducted, missing data at that time is not complemented. However, entry data compliment may be conducted in some items, and therefore, data complement method is defined in items in Chapter 10 or later chapters if any entry data complement is needed.

